#### Pregnancy Related Anxiety Questionnaire

---

A growing body of research suggests that elevated anxiety during pregnancy is a specific predictor of negative mental health outcomes for women and children. The Pregnancy Related Anxiety Questionnaire (PRAQ-R) assesses three subscales of anxiety that are specific to pregnancy; fear of giving birth, fear of bearing a disabled child, and pregnancy-related concerns about one's appearance. It is used in this evaluation at the 26-36 weeks' antenatal time point.

#### Maternal Antenatal Attachment Scale

---

The developing relationship between the mother and the foetus will be measured using the Maternal Antenatal Attachment Scale (MAAS). It consists of 19 items divided over two subscales: "Quality of Attachment (QA)" (11 items) and "Intensity of Preoccupation (IP)" (8 items). The subscale QA measures the quality of the mother's affective experience towards the unborn child (such as feelings of closeness and tenderness versus feelings of detachment and distance or irritation). The second subscale IP assesses the strength of feelings toward the unborn child and the amount of time thinking or dreaming about and talking to the foetus. All items are scored on 5-point Likert scales. The minimum score for the Global Attachment (i.e., Total) MAAS (GA) score is 19 and the maximum score is 95. The scores of the subscale QA range between 11 and 55 and

those of the subscale IP vary between 8 and 40. On both subscales and the GA, higher scores reflect a positive quality of attachment and a high preoccupation with the unborn child.

### [Mother-to-Infant Bonding Scale](#)

---

The Mother-to-Infant Bonding Scale (MIBS) will assess the feelings of the mother towards her new baby at the 2-month postnatal time point. Some mothers find it hard to relate to their new baby, and such failure may have long-term effects on the child. The MIBS is a simple 8-item self-rating tool and is acceptable for use with mothers and provides significant correlations with their early mood.

### [Mothers Object Relations Scale](#)

---

Assessment of maternal perceptions of infant warmth and invasion towards the mother, and identification of any potential attachment difficulties, will be assessed using the 14 item self-score Mothers Object Relations scale (MORS), designed to provide information about the mother's views of her baby. The MORS is commonly used as a screening tool to ensure that mothers are not suffering from clinically significant levels of either anxiety or depression. During the evaluation, it will be included at the 4-months postnatal time point.

### [Edinburgh Postnatal Depression Scale](#)

---

Symptoms of emotional distress and depression in the mother during the postnatal period will be assessed using the STAI and the Edinburgh Postnatal Depression Scale (EPDS) at the 4-months postnatal time point. The EPDS is a 10 item self-report measure and a score of 10-30 indicates varying degrees of emotional distress and depression, with a score of 30 being the most severe. The measure includes one question about suicidal thoughts. If a respondent answers yes to this question, the researcher will be alerted to make further enquiry about the nature of any thoughts of self-harm in order for the level of risk to be determined and appropriate referrals made where indicated to ensure the safety of the mother and baby.

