### 9.4 Identification of Families in Need of Support

The data collection will involve survey questionnaires comprising a range of standardised and validated questions asking about a range of aspects of parental wellbeing including mental health; substance use and experience of domestic violence. This may result in the identification of families who have additional support needs. We will routinely provide all families with an information sheet listing core local helplines and services. Trained researchers will also provide emotional support at the time of the interview and encouragement to contact their GP or health

---

 <http://www.maternityaction.org.uk/wp/wp-content/uploads/2013/09/eocpregnancydiscrimwomensurvey.pdf>

 <http://www.nspcc.org.uk/globalassets/documents/evaluation-of-services/evaluation-preventing-non-accidental-head-injuries-nahi-programme-impact.pdf>

visitor where appropriate. In the event that we identify a child who may be at risk of harm, the relevant social services will be informed.

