### 9.5 Inclusion of participants who have English language difficulties

In order to capture the experiences and attitudes of as many different ethnic groups as possible, we propose to use the following processes to try and include those who would not be able to complete an interview in English.

For the longitudinal cohort surveys, we will translate the participant-facing materials (including consent forms, invitation letters and information leaflets) into the most prevalent languages spoken in the fieldwork areas and these will be available for participants on request. As midwives and other health professionals are identifying and recruiting the sample for the cohort surveys, they will be well placed to identify any English language difficulties at the time of recruitment so that the survey information can be given in the most appropriate language.

The sample for the baseline surveys is generated differently from the cohort surveys – from a commercial sampling frame via Emma’s Diary, the largest pre-natal database in the UK – and we do not propose to translate participant-facing materials for the baseline. The sample is generated from pregnant women or mothers who sign up to Emma’s Diary via one of their communication platforms, such as their website or pregnancy guide. As all of Emma’s Diary communications are in English only, we have assumed that anyone signing up is proficient enough in English to be able to understand survey materials in English.

However, we will try and conduct interviews in languages other than English if necessary in both the main baseline and cohort surveys. If an interviewer identifies a participant who is willing to take part in the survey but is unable to do so in English, Ipsos MORI will attempt to use an appropriate bilingual interviewer to conduct the interview in the participant’s preferred language.

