As it would not be appropriate to give the CAPI machine to participants who have English language difficulties to do the self-completion section of the interview themselves, interviewers will be asked to administer the questions in this section to participants in all non-English interviews. Therefore, all interviews that are conducted in a language other than English will be entirely interviewer-administered. As the questions in the self-completion section are more sensitive and it may become obvious that it is not appropriate for the interviewer to continue asking them, a code will be added to each question that will allow the interviewer to skip the remainder of the self-completion section if necessary. In addition, and as with all the questions asked in the interview, participants are allowed to refuse any that they do not wish to answer.

As it is so important that questions from non-adapted validated measures are asked in exactly the same way and consistently across all interviews, independent translations of these sections will be made onto paper for interviewers to read out at the appropriate points within the interview. Responses will be entered by the interviewer into the (English) CAPI script. This includes any non-adapted validated measures included in the self-completion section, so the interviewer will need to read the questions and answers (where appropriate) from the translated paper version in these instances.

This means that translations onto paper would be made for the following sections in face-to-face interviews across the baseline and cohort surveys:

Cohort Pilot	Main Baseline	Main Cohort	
26-36 week questionnaire	Age 1, 2, 3 questionnaire*	26-36 week questionnaire	Age 1, 2, 3 questionnaire*
1. Edinburgh Postnatal Depression Scale (EPDS)	1. Adaptive Social Behaviour Inventory (ASBI)	1. Edinburgh Postnatal Depression Scale (EPDS)	1. Adaptive Social Behaviour Inventory (ASBI)
2. EQ-5D-5L (health outcomes)	2. Brief Infant Toddler Social Emotional Assessment (BITSEA)	2. EQ-5D-5L (health outcomes)	2. Brief Infant Toddler Social Emotional Assessment (BITSEA)
3. Maternal Antenatal Attachment Scale (MAAS)		3. Maternal Antenatal	

4. Pregnancy Related Anxiety Questionnaire (PRAQ)	3. Edinburgh Postnatal Depression Scale (EPDS)	Attachment Scale (MAAS)	3. Edinburgh Postnatal Depression Scale (EPDS)

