5. State-Trait Anxiety Inventory (STAI).	4. EQ-5D-5L (health outcomes)	4. Pregnancy Related Anxiety Questionnaire (PRAQ)	4. EQ-5D-5L (health outcomes)
	5. Strengths and Difficulties Questionnaire (SDQ)	5. State-Trait Anxiety Inventory (STAI).	5. Strengths and Difficulties Questionnaire (SDQ)

*\*Although the Sure Start Language Measure (SSLM) and British Ability Scales are included in the baseline and cohort Age 1, 2, 3 questionnaires without adaptation, they are not included in the paper translation list above because translation is not appropriate as both are tests of English vocabulary.*

At survey time-points which involve collecting data via methods other than face-to-face interviews (e.g. online), participants will be able to request to complete the survey in a different language via a translated paper questionnaire.

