- In the event that the interviewer becomes aware of any risks to the safety of a child in the home, the relevant social services department will be informed. Participants will be made aware in the information sheet that all information that they provide will be confidential unless there are concerns about the safety of the child under which circumstances the information may be shared under the terms of the Children Act 1989.

 However, using self-completion methods will not be possible for interviews conducted in languages other than English as the interviewing script will be in English only – please refer to Section 9.5 for more details of the processes we will follow in the case of a non-English interview.

- In the event that the interviewer is made aware of any substance use by the participant or, risk of domestic violence, the interviewee will be provided with relevant information about accessing support.

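### At 4 months a self-harm answer on a self-completed translated paper form raises no alert until the form is returned and read, and the stated confidentiality exception does not cover serious risk to the mother herself

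*Protocol*

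**What the plan says.** Protocol section 5.7.3, under the Edinburgh Postnatal Depression Scale, schedules the scale at 4 months postnatal and notes that one of its ten items asks about suicidal thoughts. The stated response is: "If a respondent answers yes to this question, the researcher will be alerted to make further enquiry". The researcher establishes the level of risk, with "appropriate referrals made where indicated to ensure the safety of the mother and baby".

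Table 1 collects the 4-month cohort wave by telephone or online. For waves that are not face-to-face, section 9.5 adds that "participants will be able to request to complete the survey in a different language via a translated paper questionnaire". For face-to-face waves the same section says that "all interviews that are conducted in a language other than English will be entirely interviewer-administered", and that where a woman cannot be interviewed in English "Ipsos MORI will attempt to use an appropriate bilingual interviewer".

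On confidentiality, section 9.6 says the information sheet will make participants aware that "all information that they provide will be confidential unless there are concerns about the safety of the child". Section 9.4 matches this: "In the event that we identify a child who may be at risk of harm, the relevant social services will be informed". Section 9.6 also lists a response that begins "In the event that the interviewer is made aware of any substance use by the participant or, risk of domestic violence"; it consists of giving the woman information about support.

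**The concern.** The self-harm response works only if somebody learns of the answer and is then free to act on it. Two rules elsewhere in the protocol weaken one or the other of these conditions.

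First, the only wave named for the EPDS in section 5.7.3 is one at which section 9.5 allows self-completion on paper in another language. Nobody sees a paper answer when it is given.

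Secondly, the referral is meant to protect the mother as well as the baby, but the only exception to confidentiality that the protocol describes concerns the child. A researcher who judges a mother to be in serious danger from herself, and who does not have her agreement, has one section pointing towards referral and another pointing towards silence.

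What is at stake is participant safety. The paper route falls on women with limited English. The confidentiality point could arise for any participant.

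**Working it through.** No calculation applies. The point depends on no rate, effect size, error level or sample size, so the check is to set the provisions side by side.

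**The paper route**

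1. Wave: section 5.7.3 gives the EPDS, with the suicidal-thoughts item, at 4 months.
2. Mode: Table 1 makes the 4-month cohort wave telephone or online, so it is not face-to-face.
3. Language: section 9.5 allows a translated paper questionnaire on request at waves that are not face-to-face. From steps 1 to 3, the item can be answered on self-completed paper. This is an inference. The list of translated measures in section 9.5 is for face-to-face interviews, and no section shows the 4-month translated form.
4. Timing: the trigger in section 5.7.3 is the answer. On paper the answer becomes known only when the form has been returned and somebody has read it.
5. Handling: no section says who reads returned forms, how soon, or in what language the further enquiry would be made.
6. Contrast: in face-to-face interviews the interviewer reads the translated measures aloud and keys the answers, so the researcher knows at once. The gap is confined to self-completed paper.

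**The confidentiality statement**

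| Situation after a yes | Referral under 5.7.3 | Exception as described in 9.6 |
|---|---|---|
| Mother agrees to referral | Provided for | No exception needed |
| Mother does not agree; concern about the child | Provided for | Covered |
| Mother does not agree; serious risk to herself; no concern about the child | Provided for where indicated | Not covered |

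The two sections conflict only in the last row. Section 9.4 does not resolve it, because it provides for informing social services only about a child. The rest of section 9.4 offers helpline details, emotional support at interview and encouragement to contact the GP or health visitor. None of these is a basis for sharing information without the mother's agreement.

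**Size**

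The protocol gives no 4-month target, no share of women using paper and no rate of positive answers. The number of women affected therefore cannot be derived from it.

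**The case against.** The case on the other side has real force.

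- **Timing.** A reader might infer that the protocol promises an immediate alert which paper then breaks. It does not: section 5.7.3 sets no time limit, and a returned form can still raise an alert when it is read. Paper delays the response, and nothing limits the delay. That narrower statement stands, because establishing risk in order to keep someone safe loses its value as time passes.
- **Narrowness.** Paper is on request, only for completion in another language, and the 4-month wave also offers a telephone interview. This is accepted, and it is why the number affected is probably small.
- **Self-harm is absent from the list of actions in section 9.6.** A reader might infer that the protocol has no plan for it. That is not supported, because section 5.7.3 is itself the plan. The difficulty is how that plan meets the paper route and the confidentiality statement.
- **Confidentiality.** At 4 months the mother is normally caring for an infant, so serious suicidal risk will often also be a concern about the child and be covered. The conflict shrinks to the last row of the table but does not vanish. The information sheet was not available and may be wider, although section 9.6 describes it as limited to the child.
- **Detail held elsewhere.** Section 7.1.2 refers to established participant-safety protocols, and section 9.6 to an Advisory Group with adult mental health skills. A procedure for returned forms may therefore exist, so it cannot be said that there is none. Such a procedure could shorten the delay after receipt; it could not raise an alert before the form is read.

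**Conclusion.** The point holds in a limited form. On self-completed translated paper at 4 months, a yes to the suicidal-thoughts item is unknown to the study until the form is returned and read, and the protocol states no check on receipt. Separately, the confidentiality statement conflicts with the referral when a mother is at serious risk to herself, does not agree to referral, and no concern about the child applies.

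The first part assumes that the translated 4-month form carries the EPDS, which follows from the sections read together but is not stated outright. The second assumes that the information sheet says what section 9.6 reports. The documents do not support reading this as a general failure of the self-harm response: telephone and face-to-face interviews, and referral with the mother's agreement or for the child's sake, are unaffected.

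The number of women affected is unknown and probably small, but the possible harm to any one of them is grave. Estimates, power and error rates do not change. Severity is minor to should-fix.

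**What to change.** 1. **Confidentiality.** Extend the exception in section 9.6 to serious risk of harm to the mother, and change the information sheet to match if it does not already say so.
2. **Mode at 4 months.** For women who need another language, give the whole EPDS by telephone, which is already a 4-month mode, with a bilingual interviewer where one is available. Move the scale as a unit: taking one item out of a validated ten-item scale would split its mode of administration.
3. **Where paper is still used.** Require each returned form to be checked for this item on the day of receipt, with call-back by the field agency, which holds the identifiers (section 6.1.1).

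The cost is a little more fieldwork, because bilingual interviewers are at present described for interviews and would also be needed by telephone. Protocol wording, and possibly information-sheet wording, would change. No extra participants are needed. Answering aloud rather than on paper, and a wider exception, may slightly reduce disclosure. The clinical content of the response is for the sponsor to decide.

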### [Primary Care Post Traumatic Stress Disorder Screen](#)

---

The Primary Care Post Traumatic Stress Disorder (PC-PTSD) is a 4-item screen that was designed for use in primary care and other medical settings. The screen includes an introductory sentence to cue respondents to traumatic events. The authors suggest that in most circumstances the results of the PC-PTSD should be considered "positive" if a patient answers "yes" to any 3 items. Those screening positive should then be assessed with a structured interview for PTSD. The screen does not include a list of potentially traumatic events. Respondents in the evaluation will be asked to complete the screen as part of the 4-months postnatal survey to assess the occurrence of any recent traumatic events, including, but not limited to, the birth of their baby.

### [Brief Infant and Toddler Socio-emotional Adjustment Scale](#)

---

Infant social and emotional adjustment will be assessed using the Brief Infant and Toddler Socio-emotional Adjustment Scale (BITSEA), which comprises a 42-item parent-report measure of infant and toddler (that is, 1- to 3-year-old children) social and emotional adjustment. It comprises two subscales – competence and problems measured using a three-point Likert scale. A higher score for the competence subscale and a lower score for the problems subscale indicate better adjustment. It also discriminates children with clinically significant problems from matched subjects.

### [Sure Start Language Measure](#)

---

The Sure Start Language Measure (SSLM) is a parental report measure of early language development. It measures English vocabulary knowledge (the original assessment was based on a list of 100 words) alongside a measure of parental concern about language and other cognitive and social development. The most recent version of the SSLM will be used for this study. It comprises a reduced list of 50 words and four questions about parental concerns (Harris, Law and Roy, 2005), which the authors concluded is easier and quicker to use and addresses differences seen when using the 100-word format between children of different language. A higher score indicates more advanced language development.

### [Strengths and Difficulties Questionnaire](#)

---

The Strengths and Difficulties Questionnaire (SDQ) is a brief behavioural screening questionnaire for use with children aged from 3 to 16 years. The SDQ includes 25 items on psychological attributes, measured using a 3-point Likert scale (not true, somewhat true, certainly true). Separate versions exist for parents and for teachers/educators, who are asked the extent to which each

descriptor (e.g. considerate of other people's feelings) is true for the child in question. For older children (11+) there is also a self-completion version. The items are organised into 5 scales, each with 5 items: emotional symptoms, conduct problems, hyperactivity/inattention, peer relationship problems (totals of these 4 scales added to generate a total difficulties score out of 20) and pro-social behaviour. A higher score denotes more difficulties on the four 'problem' subscales.

### [British Ability Scales \(II\)](#)

---

The British Ability Scales (II) battery is an educational psychology tool that provides a reliable standardised measure of children's cognitive and linguistic functioning, and has been adapted for use by survey interviewers. The evaluation will use two subscales of the BAS assessments - 'naming vocabulary' and 'picture similarity', the first being a measure of vocabulary and the second being a measure of non-verbal reasoning ability. Scores are age adjusted.

### [Adaptive Social Behaviour Inventory](#)

---

The Adaptive Social Behaviour Inventory (ASBI) is an instrument based on 30 questions, developed to assess multiple dimensions of social competence in young children, using parents or educators as raters. For this research, we propose using the 5 factors identified in the EPPE research: compliance, pro-social, confidence, anti-social and anxiety (Sammons et al, 1999: EPPE Technical Paper 2). A higher score denotes more problems (antisocial and anxiety) or more strengths (compliance, pro-social, confidence).

## 5.7.4 Bespoke Questions and Adapted Measures

### [Toddler Home Learning Environment Index and HOME Short Form](#)

---

Evidence suggests that parental involvement in early learning has a greater impact in children's wellbeing and achievement than any other factor, such as family income, parental education or school environment. The evaluation will use selections from the Toddler Home Learning Environment (HLE) index and HOME short form (SF), used in previous longitudinal studies, at ages 1, 2 and 3, to assess the home learning environment of the child. The questions focus on educationally orientated activities such as reading to the child, playing and learning activities with letters, numbers and shapes, painting and drawing and visiting the library. A higher score denotes a more supportive home learning environment.

